Since conservative treatment is not always effective,^{1,20} rotator cuff repairs are commonly used surgical procedures^{1,4,25,26,10,15,17,20-24} and a procedure that is becoming more frequent in advanced ages.^{22,27}

Rehabilitation plays an essential role in the recovery of rotator cuff repair,^{8–10,13,15,20,28–31} and should be customized to the patients characteristics and needs.^{15,18,20,32} Different aspects must be taken into consideration for functional recovery, such as age, activity levels, extent and location of the tear, duration of symptoms, prior muscle atrophy or fatty infiltration and concomitant pathologies.^{10,17,20,23,24,31,33}

The primary goal of the rehabilitation is to relieve pain, restore function, range of motion, strength,^{4,20,29,31,34–36} balancing the need of protecting the repair and the need of mobilization to avoid stiffness and restore normal function and kinematics.^{15,20,30,31,37,38} This balance, however, is very delicate, as re-tears or failed healing are very common after surgery^{22,25,27,39}, and therefore therapies must focus on improving function without compromising the healing process.^{15,27,31}

Assure an early passive range of motion is recommended by many authors to prevent stiffness, one of the most frequent complications after rotator cuff repairs^{15,37,38,40–42} as well as joint adhesions and further tendon degradation. Conversely, longer immobilization periods can promote tendon healing and reduce the rates of re-tear.^{32,37,38,43} There is no consensus on this matter, with an immobilization period of 6 weeks being the most common period advised.^{20,28} However, several studies found no differences between them in function, pain, ROM or re-tears ratio, concluding that early mobilization may be beneficial.^{22,23,28,30,34,37,38,40,41} Furthermore, some studies demonstrate that early initiation of rehabilitation with active exercise does not appear to affect patient-reported pain and disability outcomes in a short (≤ 3 months), mid (6

SH-RCT-ARCR-01 Study Protocol

months) or long-term period (≥ 12 months).^{8,9,36} Still, even within the early mobilization group, there is no consensus on how early should the mobilization begin - since day one to 2 days after, 1 week after, 5 weeks after.^{4,28,41}

Apart from the discussion between early or late passive mobilization, there is also no consensus on which rehabilitation programs are better.^{8–10,15,17,26,38} Several studies and systematic reviews have been published on the subject, focusing mainly on the times of progression.^{4,8,40–42,44,45,23,28–30,32,34,37,38} These studies all define a four-stage process consisting of: a) immobilization, b) passive range of motion; c) active range of motion and d) strengthening, with variable times of progression.^{9,15,20,28,33} The total duration of the rehabilitation process is also variable, with some studies stating that it might take up to 6-12 months to regain full strength.^{4,33,35}

Regarding rehabilitation setting, some studies suggest that home-based therapy, based on exercise, could be as effective as clinic-based interventions.^{21,26,46,47} This is in line with the recent trends in healthcare delivery, away from inpatient care and towards home-based care with the intent of improving cost-effectiveness.

Given the high incidence and prevalence of shoulder rotator tears, and the associated morbidity, which represents a huge economic burden^{3,16,48} it is essential to ensure the access to cost-effective rehabilitation.⁴⁷ In this regard, digital health solutions that empower patients, maximize engagement and allow home-based rehabilitation without the need for constant therapist supervision, could improve effectiveness and lower the cost of rehabilitation.

SH-RCT-ARCR-01 Study Protocol

SWORD Health has developed a novel digital biofeedback system for home-based physical rehabilitation (SWORD Phoenix®). Using inertial motion trackers, this system digitizes patient motion and provides real-time feedback on performance through a mobile app. It also includes a web-based platform that allows the clinical team to prescribe, monitor and adapt the rehabilitation process remotely. This way, the system allows patients to perform independent rehabilitation sessions at home without the need for constant therapist supervision, ensuring remote monitoring throughout the rehabilitation program.

2. Study Objective

The objective of the present study is to evaluate the clinical outcomes of a home-based rehabilitation program using this system against conventional home-based rehabilitation after arthroscopic rotator cuff repair. We hypothesize that the clinical outcomes of such a program will be at least similar to those of traditional rehabilitation.

3. Study Design

This study is a single-center, prospective, non-blind, parallel-group, randomized controlled trial with an active comparator.

4. System technical specifications

The version of SWORD Phoenix used in this study is composed of the following components:

- a) **Inertial motion trackers:** each one is composed of a three-axis gyroscope, three-axis accelerometer and a three-axis magnetometer, allowing 3D

Version 2.0

Date: 06/14/2018

movement analysis and quantification. The trackers communicate via Bluetooth LE with a tablet computer.

- b) **Mobile App:** a mobile app that processes the information generated by the motion trackers and provides real-time biofeedback regarding movement quality and patient performance.
- c) **Web-based Portal:** a web-based platform that allows the clinical team to prescribe motor tasks and monitor results.

Motion Trackers

The motion trackers are placed on body segments using Velcro® straps. Each motion tracker is placed in a specific position. To assist in the correct placement of the motion trackers, both the trackers and the matching straps are color-coded. In this study, the following setup will be used:

- **Red tracker:** over the sternal manubrium
- **Green tracker:** on the medium third of the external surface of the upper arm, pointing to the elbow
- **Blue tracker:** on the dorsal surface of the distal third of the forearm, pointing to the hand

Mobile App

The mobile app guides the patient in each exercise session. Before each exercise, the

patient is presented with a real-life video and audio explanation of that exercise. The execution interface is subsequently shown. This screen features: a) a posture dummy indicating correct/incorrect posture; b) a progress bar; c) a timer indicating rest time between repetitions and prompting start when rest time is over; d) a repetition counter; e) a star counter and f) a timer displaying time left to complete the exercise.

Only correctly performed repetitions count towards the repetition counter. A correct repetition is defined as a movement starting at the baseline and reaching or surpassing the specified target, without violating movement or posture constraints. In case the patient violates a movement constraint, a message is prompted showing which movement error was performed, so that the patient can correct the movement in the following attempts.

For each correct repetition, the patient earns from 1 to 3 stars, depending on how much he was able to surpass the target, as long as he has not violated any movement or posture constraints.

Web Portal

The portal is a web-based platform that allows the clinical team to create new patient profiles and create exercise sessions for each patient. When a patient performs a session, the results are uploaded to the platform and available for review. Based on this information, the clinical team can edit the parameters of each session and exercise according to patient performance and progress.

5. Study Outcomes

The assessment of the effectiveness of treatments in shoulder conditions is complex^{49,50} and should include not only the traditional clinical outcomes, such as

joint measures, but also the assessment of functional deficits, through patient reported outcome measures.⁴⁹⁻⁵¹ Lately, there has been a shift towards the latter, which are currently the primary outcomes of most research studies.⁴⁹

The Constant Shoulder Score is one of the most used outcome assessment tools worldwide,^{49,50,52,53} maybe due to the fact that it's psychometric properties have been widely studied,⁵⁰ and that it includes essential measures - physical assessment of strength and motion - as well as patient-reported function.^{49,52,53} Additionally, it is considered, in some studies, as a gold standard or "reference scale",⁵¹ and its extensive use allows for comparisons between study samples and results.⁴⁹

The DASH questionnaire also provides a very accurate assessment⁵¹ and has been recommended to be the first line of assessment in shoulder disorders, due to its high responsiveness and well-established benchmarks.⁵² The QuickDASH, its short version, with 11 items, is also validated, and its psychometric properties are very high and similar to the original long version.^{52,54} The use of QuickDASH was analysed in patients with a rotator cuff repair and was recommended to assess patients who underwent a surgery process,⁵⁴ therefore applicable in the present context.

Although the use of patient-reported outcome measures is highly recommended, conventional measures such as range of motion are still clinically relevant and critical part of shoulder assessment.^{17,52} Shoulder flexion, abduction, internal and external rotations are the mainly cited movements, although with high variability in the positions of measure.⁵²

Based on this evidence, the following outcomes will be measured:

- a) functional assessment – Constant Score
- b) patient-reported outcomes - QuickDASH

- c) range of motion of the shoulder (in degrees)

The outcome measures will be assessed pre-operatively, and then at 6, 12, 16 and 20 weeks after the surgery. In patients where a decision is made to extend the program to 24 weeks, another assessment will be made at this point.

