5.2 Secondary outcomes

The secondary outcomes will be:

- The change in patient reported function in comparison to the baseline, measured by the QuickDASH score
- The change in shoulder range of motion in comparison to the baseline, measured by the shoulder flexion degree in a sitting position (in degrees)

6. Sample size estimate

Sample size estimation was performed taking into consideration the primary outcome measure – The Constant Score - and a non-inferiority scenario.

In the absence of similar studies, the calculations were made taking into account the study by Arndt *et al.* (2012)⁴⁰. This was a large study (n=100 patients) which compared two different rehabilitation protocols after ARCR and which used the same primary outcome as our study. In this study, the standard deviation of the Constant

Score at baseline was 12.0. A Minimal Clinically Important Difference (MCID) of 10.4 was considered, based on the study by Constant *et al.* (2008).⁵⁵

Considering a power of 90%, a two-sided 0.05 significance level and a 10% dropout rate, 68 patients would be necessary to detect a 10.4 points difference between the two groups.

7. Location of Recruitment

Patients will be recruited at Hospital da Prelada - [name] da Cruz.

8. Inclusion criteria

- a) Patients over 18 and under 70 years old
- b) Shoulder pain and functional limitation with clinical examination compatible with reparable rotator cuff tear
- c) Imaging (MRI or ultrasound) evidence of rotator cuff tear (supra and/or infraspinatus tendon tear inferior to 5cm)
- d) Indication for a rotator cuff repair according to the patient's orthopedic surgeon
- e) Ability to understand simple and complex motor commands
- f) Availability of a carer to assist the patient after surgery

9. Exclusion criteria

Preoperative

- a) Patients with indication for revision cuff repair
- b) Complex cuff tears (involving subscapularis tendon or more than one tendon besides supra and infraspinatus, or massive dimension tears)

- c) Glenohumeral arthritis
- d) Irreparable tendon defect
- e) Patients with concomitant neurological disorders (ex. Stroke, Parkinson's disease, multiple sclerosis)
- f) Aphasia, dementia or psychiatric comorbidity interfering with the communication or compliance to the rehabilitation process
- g) Respiratory, cardiac, metabolic conditions or others incompatible with at least 30 minutes of light to moderate physical activity

Postoperative

- h) Irreparable tendon lesion

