- i) Major medical complications occurring after surgery that prevent the discharge of the patient within 5 days after surgery
- j) Other medical and/or surgical complications that prevent the patient from complying with a rehabilitation program
- k) Blind and/or illiterate patients

10. Methods for identifying and recruiting patients

All patients admitted for rotator cuff repair during the study period will be screened for inclusion and exclusion criteria.

When a potential candidate is identified, the local investigator will approach the candidate and explain the study in detail. The prospective candidate will be given the patient information document and sufficient time to consider whether he wishes to participate in the study.

Subsequently, the prospective candidate will be given opportunity to clarify any

doubts, after which the informed consent form will be signed and dated in duplicate by the patient and the investigator. Only then will the randomization and baseline assessments be performed.

11. Patient allocation to study groups

For logistic reasons, the study will be restricted to patients living in a 20km radius around the investigation center. Patient allocation to the two groups will be performed in a random way, in a 1:1 ratio in blocks of six. This will be done using an online randomizer (<https://www.randomizer.org>).

The allocation of patients to each group will be performed centrally by one investigator - [name] - and communicated to the responsible for data acquisition only after patient enrollment. This investigator will not be involved in data collection or in outcomes assessment.

12. Blinding

The nature of the study does not allow blinding of the patients regarding study groups. However, participants will be blinded to the primary and secondary outcomes being measured. All patient assessments will be performed by an investigator blinded for randomization groups. Statistical analysis will be performed blinded for randomization group.

13. Patient assessment

Patients will be assessed pre-operatively, and then at 6, 12, 16 and 20 weeks after the surgery. In patients where a decision is made to extend the program to 24 weeks,

another assessment will be made at this point. An assessment will also be made at 12 months after surgery.

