13.1.3 Shoulder range of motion

The shoulder range of motion will be measured in the sitting position.

The system used in the study is a validated medical device for joint angle measurement. Therefore, shoulder range of motion will be measured automatically

SH-RCT-ARCR-01 Study Protocol

by the system.

In this study, active range of motion will be measured in the following movements:

- a) Elevation of the shoulder in the scapular plane, sitting: with the patient sitting, with the arm fully extended, have the patient actively raise the arm in the scapular plane as much as possible, with extended elbow.
- b) Sitting shoulder flexion: with the patient sitting, with the arm fully extended, have the patient actively raise the arm as much as possible, with extended elbow.
- c) Sitting Shoulder Abduction: with the patient sitting, with the arm as close as possible to the body, have the patient actively open the arm as much as possible, with extended elbow.
- d) Sitting Shoulder External Rotation: with the patient sitting with 90° bent elbow and hand pointing forward, have the patient actively rotate the arm outwards, as much as possible.

In order to achieve this, the investigator will need to:

- 1) Create a new patient in the Phoenix Portal
- 2) Prescribe these four different exercises, described above
- 3) Setup SWORD Phoenix
- 4) Ask the patient to perform five repetitions of each movement to the best of his ability, while SWORD Phoenix records movement parameters
- 5) After the session, login to the Portal, go to the session's results and click on detailed results for each exercise. Record the value of best repetition for each exercise in the patient file.

13.2 Assessments at 6, 12, 16, 20 (and/or 24) weeks after surgery and assessment

12 months after surgery

These assessments will include:

- a) Constant score
- b) QuickDASH
- c) Shoulder range of motion (as described for the baseline assessment)

14. Intervention

Both study groups will receive early-onset home-based rehabilitation for 20 weeks, starting two weeks after surgery.²⁸ This program can be extended for another 4 weeks if necessary.

The experimental group will perform daily home-based rehabilitation sessions using SWORD Phoenix, under remote monitoring by a physiotherapist, as well as home one-to-one physiotherapy sessions, with decreasing periodicity depending on program stage.

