Patients in the active comparator group will receive face-to-face rehabilitation sessions provided by a physical therapist. Therefore, patient safety will be ensured at all times during the sessions. Patients will be able to report adverse events to their physical therapist. Moreover, the patient's orthopedic surgeon will be notified in case of detrimental clinical progression, so that the patient can be re-evaluated.

For patients in the experimental group, safety of the remote sessions will be evaluated through pain and fatigue scores (graduated from 0 to 10) collected at the end of each session. These will be presented to the patient using the mobile App and will be available for remote monitoring by their physical therapist. In case of excessive pain or fatigue, patients will be contacted by their physical therapist to ascertain the cause and change prescription if needed. Patients will also be asked to report any other adverse events to their physical therapist by telephone. Moreover, the patient's orthopedic surgeon will be notified in case of detrimental clinical progression, so that the patient can be re-evaluated.

The adverse events will be registered in the patient's file (beginning date, resolution date (if applicable), resolution state, severity).

16. Statistical analysis

To assess differences in clinical and demographic variables of the patients allocated to the two study groups, independent samples t test or Mann-Whitney U test will be used for quantitative variables. For qualitative variables, Chi-squared test or Fisher's exact test will be used.

Outcome analysis will be performed using a per-protocol analysis. The impact of the interventions in the primary and secondary outcomes will be evaluated considering

the change between baseline and week 20. Differences between the two study groups will be performed using independent samples t test or Mann-Whitney U test.

Since outcomes will be measured in several different times during the rehabilitation program, a repeated measures analysis will also be performed, using a 3x2 ANOVA with group as an independent factor and time as a within-subjects factor.

17. Potential Risks and Benefits to Participants

There are no invasive procedures involved in this research protocol and, given the nature of the intervention, no relevant risks are foreseen.

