Both study groups will benefit from a 20-24 week rehabilitation program starting on week 2 after surgery. This program will be based on the latest treatment guidelines and will therefore represent the state of the art regarding rehabilitation after arthroscopic rotator cuff repairs. Thus, both study arms are likely to benefit directly from entering the study.

The experimental group will perform, in addition to the one-to-one physiotherapy sessions, a home-based program using SWORD Phoenix. This program will be tailored to their specific needs and be accompanied remotely by a physical therapist, that will have access to patient performance data, as well as pain and fatigue scores as rated by the patient at the end of each session. This allows the therapist to detect adverse events and to act promptly. In case of detrimental clinical progression, the patient's orthopedic surgeon will be notified, and the patient will be re-evaluated, to decide whether to continue the study. This ensures patients in the experimental group are not subject to greater risk.

Participants will not receive any payments or reimbursements specifically for taking part in this study.

18. Confidentiality of Personal Data

Data collection for this study was authorized by the National Commission on Data Protection, with the authorization number 5798/2018.

Personal data will only be accessible to authorized investigators in this study.

Personal data will not be entered into the database as part of this research. The clinical data collected will only be linked to the patient by a unique study number and will contain no personal identifiers. Informed consent will be obtained from participants to collect and retain this data. The data that will be used for analysis and dissemination for research purposes will be completely anonymized.

19. Ethical issues

All participants will be provided with information about the purpose and procedures of the study and will give written informed consent before inclusion.

The study was approved by the Ethics Committee of Hospital da Prelada (Authorization number 42-26/06/2018).

20. Dissemination of Results

The results of the study will be published in peer-reviewed scientific journal(s) and presented at relevant national and international meetings.

References

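### No visit, including the one at 12 months, asks about re-tear, re-operation or other adverse events; spontaneous reporting differs by arm, and no comparison of events by arm is planned

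*Combined protocol and SAP*

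**What the plan says.** The background text before Section 2 treats repair integrity as the central hazard of rehabilitation. It says that "re-tears or failed healing are very common after surgery", describes "stiffness, one of the most frequent complications after rotator cuff repairs", and asks that therapy improve function without harming healing.

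Section 13 sets visits at 6, 12, 16 and 20 weeks (24 if the programme is extended) and adds: "An assessment will also be made at 12 months after surgery". Section 13.2 gives one list for all of these visits. It has three items: Constant Score, QuickDASH and "Shoulder range of motion (as described for the baseline assessment". For that third item, Section 13.1.3 states that "active range of motion will be measured in the following movements", and names four movements. One of them is a secondary outcome in Section 5.2: "The change in shoulder range of motion in comparison to the baseline, measured by the shoulder flexion degree in a sitting position".

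Section 15 covers safety. Comparator patients may report adverse events to their physical therapist. Experimental patients give pain and fatigue scores after each remote session, and "Patients will also be asked to report any other adverse events to their physical therapist by telephone". In both arms the surgeon is told of detrimental progression. Events go into the patient file with dates, resolution state and severity. Section 16 compares the outcome scores, with the main comparison at week 20, and does not mention adverse events.

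**The concern.** The trial replaces a large part of therapist contact with sessions that patients do alone with a device, and it hopes to show outcomes at least as good as conventional care. The harms that the protocol itself calls common are the ones that a reader of such a result would ask about first. Three gaps combine:

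- No one is scheduled to ask about re-tear, re-operation, treatment for stiffness or any other event.
- Events depend on patients volunteering them to a therapist, and the chance to do so differs by arm.
- No route is described between the end of the programme and 12 months, and the 12-month visit does not make up for this.

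Followed as written, the trial could report similar Constant Scores at week 20 with no harm data that can be compared between arms. A low count in the experimental arm could reflect fewer events or fewer occasions to mention them, and the data would not distinguish the two.

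**Working it through.** **1. What each visit collects.** The Section 13.2 list was set against the harms named in the background.

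- Re-tear or failed healing: no item at any visit.
- Re-operation: no item at any visit.
- Stiffness: measured indirectly. Active motion in four movements is recorded at every visit, and the Constant Score (Section 13.1.1) has a motion component. No stiffness event, threshold or passive measure is defined, and reduced active motion alone does not separate stiffness from other causes.
- Other adverse events: no enquiry at any visit.

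**2. Contact by arm.** The session schedule at the end of Section 14 gives these totals, which reproduce:

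- Conventional: 4 + 15 + 15 + 18 = 52.
- Experimental: 2 + 9 + 5 + 3 = 19.
- Ratio: 52 / 19 = 2.7. Reduction: (52 − 19) / 52 = 63%.

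The schedule describes the normal course without exceptions. The other reporting channels also differ: telephone reporting and session pain and fatigue scores are described for the experimental arm only.

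**3. Time without a described route.** The end of the programme can be read in two ways.

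- Session schedule: week 20, or 24 if extended. Remaining in the year: 52 − 20 = 32 weeks (62%), or 52 − 24 = 28 weeks (54%).
- Opening of Section 14 taken literally (20 weeks of rehabilitation beginning in postoperative week 2, plus 4 if extended): week 22 or 26. Remaining: 52 − 22 = 30 weeks (58%), or 52 − 26 = 26 weeks (50%).

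On either reading, half or more of the first year has no described reporting route.

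**4. What collection could show.** This step sizes the remedy, not the defect. The inputs are the planned total of 68, 1:1 allocation and 10% dropout (Sections 6 and 11), giving 68 × 0.9 / 2 = 30.6 evaluable patients per arm. The documents give no re-tear rate, so a common rate p of 10% to 40% is assumed.

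Half-width of the 95% interval for the difference = 1.96 × √(2p(1 − p) / 30.6):

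- p = 10%: 1.96 × √(0.18 / 30.6) = 15 points
- p = 20%: 1.96 × √(0.32 / 30.6) = 20 points
- p = 30%: 1.96 × √(0.42 / 30.6) = 23 points
- p = 40%: 1.96 × √(0.48 / 30.6) = 25 points

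If all 34 per arm were followed, the range would be 1.96 × √(0.18 / 34) = 14 to 1.96 × √(0.48 / 34) = 23 points. Either way, the comparison is descriptive.

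**The case against.** The best defence is that the plan does measure harm. Several parts of it stand, and they rule out stronger readings that a reader might otherwise infer.

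- **That stiffness is not recorded.** The documents do not support this. Active motion is measured at every visit, including 12 months, and flexion is a secondary outcome. Only a defined stiffness event is missing.
- **That no harm data are collected.** This also goes too far. Section 15 requires reported events to be registered and sets no end date, so a re-tear that a patient reports would fall within it. What is missing is a scheduled enquiry, a described route after the programme, and an analysis.
- **That Section 17 makes a safety claim the trial cannot support.** The sentence "This ensures patients in the experimental group are not subject to greater risk" closes an account of monitoring and escalation. It argues that participants are protected and is not a conclusion the trial sets out to test.
- **That the wide intervals prove the defect.** They reflect the size of the trial and would be as wide with complete collection.

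It can also be said that a re-tear affecting pain or function may lower the Constant Score or QuickDASH. That is so, but a lower score does not identify its cause. Section 16 also analyses per protocol, and Section 17 allows a patient who is deteriorating to be re-evaluated on whether to continue, so such a patient might not be in the comparison.

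A last objection concerns the remedy. Section 12 blinds the assessor, and under Section 14 the patient file may hold device adherence data and records of technical-assistance contacts. A file check by the assessor could reveal the arm. This is correct, and the fix below allows for it.

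**Conclusion.** The point holds in this form: no scheduled enquiry about re-tear, re-operation or other adverse events at any visit; stiffness captured only through active motion; reporting opportunities that differ by arm (52 against 19 face-to-face sessions, with different channels); no described route for 26 to 32 weeks of the first year; and no analysis of events by arm. The consequence is that an excess of clinically detected re-tears or re-operations in either arm could be missed or counted unequally.

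The documents do not show that the experimental programme is less safe, and this point does not claim so. Nor does it affect the calculation of the primary comparison. The week counts rest on the protocol's own schedule and on its two readings of the programme's end. The interval widths rest on assumed event rates and only show what a descriptive table could deliver. The change is worth making because it is cheap and the missing information bears directly on how a finding of similarity would be read.

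**What to change.** **Section 13.2.** At every existing visit, including 12 months and identically in both arms, add a scripted question asked after the outcome measures have been scored. It should cover, since the last visit:

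- re-tear suspected or confirmed in usual care, with no added imaging;
- re-operation on the shoulder;
- treatment for stiffness;
- any other adverse event.

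Any check of the patient file should be done by existing study staff other than the blinded assessor.

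**Section 16.** Tabulate these events by randomised arm in all randomised patients, to week 20 and to 12 months, with 95% confidence intervals for the difference, labelled descriptive.

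**Reconcile.** The opening of Section 14 and the session schedule should agree on when the programme ends. The list of assessment times in Section 5 should agree with Sections 13 and 13.2 on the 12-month visit.

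**Cost.** One form page and one table, with no extra visits, imaging or patients. Silent re-tears will still be missed and the intervals will be wide. Rewording the Section 17 sentence is optional and not needed to close this point.
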